#### **6. Statistical Analysis**

- **Sample Size Calculation**

The main hypothesis of the study was to investigate whether there is a difference in RDW levels between patients who survived and those who did not. Based on the study by Lorente et al. (2021), which reported RDW values of  $13.4 \pm 1.5$  and  $14.5 \pm 2.2$ , an effect size of 0.58 was calculated. At a significance level of 0.05 and a statistical power of 0.80, the required sample size was determined to be 110 patients in total. The sample size calculation was performed using the G\*Power software (version 3.1.9.2).

- **Statistical Methods**

Descriptive statistics will be presented as mean  $\pm$  standard deviation (min–max) for normally distributed quantitative variables, as median (min–max) for non-normally distributed variables, and as percentages for categorical variables. To compare two independent groups, the *Independent Samples t-test* will be used when assumptions are met, while the *Mann-Whitney U test* will be applied otherwise. Relationships between categorical variables will be evaluated using the *Chi-Square test*, *Fisher's exact test*, or multi-way Chi-Square test, as appropriate. For comparisons involving more than two groups, *One-Way ANOVA* or the *Kruskal-Wallis test* will be applied depending on the distribution of data. All statistical analyses will be performed using SPSS software (version 11.5).

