### 2. Objective of the Study:

COVID-19 has caused significant morbidity and mortality worldwide, particularly among critically ill patients. Early identification of patients at high risk for poor outcomes is crucial. Red cell distribution width (RDW), a measure of the variation in red blood cell size, has emerged as a potential marker of inflammation and has been associated with adverse outcomes in various medical conditions, including COVID-19.

This study aims to investigate the relationship between RDW and mortality in severe and critical patients admitted to our COVID-19 intensive care unit.

- **Primary Objective:** To determine whether RDW can serve as a prognostic marker for mortality in severe and critical COVID-19 patients admitted to the ICU.
- **Secondary Objective:** To evaluate the association of RDW with adverse outcomes such as invasive mechanical ventilation, duration of intubation, and secondary organ damage in severe and critical COVID-19 patients admitted to the ICU.

---

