### 3. Inclusion Criteria:

- Patients over 18 years of age
- Severe and critical COVID-19 patients (with positive PCR test or diagnosed clinically and radiologically)
- Patients followed in the ICU for at least three days
- Patients without hematological malignancy

COVID-19 severity was classified according to the **Diagnosis and Treatment Protocol for Novel Coronavirus Pneumonia (Trial Version 7)** published by the National Health Commission of the People's Republic of China:

- **Severe cases:** Meeting any of the following criteria:
  - Respiratory rate (RR)  $\geq$  30 breaths/min
  - Resting oxygen saturation (finger)  $\leq$  93%
  - Arterial partial pressure of oxygen (PaO2)/fraction of inspired oxygen (FiO2)  $\leq$  300 mmHg

- 50% progression of lung lesions within 24–48 hours on imaging
- **Critical cases:** Meeting any of the following criteria:
  - Respiratory failure requiring mechanical ventilation
  - Shock
  - ICU admission required due to organ failure other than respiratory failure

*Reference: National Health Commission & National Administration of Traditional Chinese Medicine. (2020). Diagnosis and treatment protocol for novel coronavirus pneumonia (Trial Version 7). Chinese Medical Journal, 133(09), 1087-1095.*

---

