#### **4. Exclusion Criteria:**

- Patients under 18 years of age
- Patients with hematological malignancies (since RDW levels may be affected)
- Patients who died within three days of ICU admission

---

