#### **5. Data Collection:**

Patient demographics, clinical features, laboratory results (including RDW), and outcomes will be collected from electronic medical records and patient files.

To ensure patient confidentiality, data will be anonymized. Since all data will be de-identified and analyzed retrospectively, no direct patient contact will be required.

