#### **Data to be recorded:**

- **Demographics:** Sex, age, body mass index (BMI), number and type of COVID-19 vaccines
- **Comorbidities**
- **Hospitalization data:** Referring department, length of stay, outcome (mortality/discharge), discharge destination
- **At ICU admission:** APACHE II and SOFA scores, days from symptom onset to hospital admission, type of respiratory support, hematological and biochemical laboratory results
- **During follow-up:** Trends in hematological and biochemical laboratory parameters (increase/decrease/normalization), need for invasive/non-invasive mechanical ventilation, duration of intubation, antiviral therapy, development of secondary infections, development of secondary organ failure, mortality/discharge

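### The primary objective is prognostic, but the planned tests give no effect estimate for death by RDW, no AUC with a confidence interval, and no severity-adjusted estimate

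*Combined protocol and SAP*

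**What the plan says.** Section 2 gives the primary objective: "To determine whether RDW can serve as a prognostic marker for mortality in severe and critical COVID-19 patients admitted to the ICU".

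Section 6, under Sample Size Calculation, states the main hypothesis as "whether there is a difference in RDW levels between patients who survived and those who did not" and sizes the study at 110 patients for that comparison. Under Statistical Methods it lists descriptive statistics, the t-test or Mann-Whitney U test for two groups, ANOVA or Kruskal-Wallis for more than two, and chi-square, Fisher's exact or multi-way chi-square tests for categorical variables. It lists no regression, odds or hazard ratio, ROC analysis, confidence interval or adjusted analysis, and no other section does.

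The data for such analyses are to be collected. Section 5 says that "laboratory results (including RDW), and outcomes will be collected". The list of data to be recorded includes age and, at ICU admission, "APACHE II and SOFA scores, days from symptom onset to hospital admission" together with laboratory results. It also includes trends in the laboratory values during follow-up. No section says which RDW value is the primary one.

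**The concern.** Whether a marker is prognostic is a question about the risk of death given the marker: how steeply risk rises with RDW, how well RDW separates those who die from those who live, and how precisely either is known. Section 6 asks the reverse question, whether mean or median RDW differs by outcome. A p-value from that comparison can be small when the separation is too weak to be useful for an individual patient.

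Age and two severity scores are recorded, yet section 6 gives them no role in any adjusted analysis of RDW. A reader of the results could not tell whether RDW says anything that APACHE II does not. At stake is how fully the primary objective is answered, not whether the planned test is sound.

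**Working it through.** **Inputs.** From section 6: RDW 13.4 (SD 1.5) and 14.5 (SD 2.2), effect size 0.58, alpha 0.05, power 0.80, total 110. Assumed here: normal distributions, a two-sided test, and the higher mean belonging to non-survivors (section 6 does not label the groups). No mortality is given, so 22, 55 and 88 deaths among 110 (20%, 50%, 80%) are used.

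**1. The plan's own figures.**
- d = (14.5 − 13.4) / √((1.5² + 2.2²)/2) = 1.1 / 1.883 = 0.584, which agrees with the stated 0.58.
- With 55 per group, a two-sided Mann-Whitney calculation using the minimum asymptotic relative efficiency (0.864) and the unrounded d gives a total of exactly 110, with power 0.805. A plain t-test would need 94 to 96. Section 6 does not say which was used. The sample size is not in dispute, but it belongs to the crude comparison only.

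**2. Discrimination implied by those inputs.**
- AUC = Φ(1.1 / √(1.5² + 2.2²)) = Φ(1.1 / 2.663) = Φ(0.413) = 0.66.
- The cut-off that maximises sensitivity plus specificity is 14.72. Sensitivity = 1 − Φ((14.72 − 14.5)/2.2) = 1 − Φ(0.10) = 0.46. Specificity = Φ((14.72 − 13.4)/1.5) = Φ(0.88) = 0.81.
- With 55 deaths and 55 survivors, this flags about 25 of the deaths (0.46 × 55) and about 10 of the survivors (0.19 × 55).

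**3. Precision with 110 patients.** The standard error of the AUC comes from simulation of the two normal distributions, and the interval is 0.66 ± 1.96 × SE. The odds ratio per 1% RDW comes from logistic fits to data simulated from the same inputs.

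| Deaths of 110 | SE of AUC | 95% interval for AUC | OR per 1% RDW (95% interval) |
|---|---|---|---|
| 22 | 0.073 | 0.52 to 0.80 | 1.48 (1.10 to 2.00) |
| 55 | 0.052 | 0.56 to 0.76 | 1.38 (1.11 to 1.72) |
| 88 | 0.057 | 0.55 to 0.77 | 1.30 (1.02 to 1.67) |

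**4. What a just-significant result would mean.** Assuming equal SDs, the smallest significant d is t(0.975; 108) × √(1/n₁ + 1/n₀), and the AUC is Φ(d/√2).
- 55/55 split: d = 0.378, AUC = 0.61.
- 22/88 split, either way round: d = 0.472, AUC = 0.63.

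**5. What the listed tests could yield.** A crude AUC could be recovered as U/(n₁n₀) if the Mann-Whitney U is reported, or approximately from means and SDs if these are given by outcome group. The plan commits to neither, and to no interval. Multi-way chi-square applies to categorical variables with no stratifier named, so it does not adjust continuous RDW for age or severity.

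**The case against.** The strongest reply is that section 6 makes the objective operational. It names a main hypothesis, sizes for it and lists matching tests. No section claims that RDW has value independent of severity, so asking for an adjusted estimate reads more into the term prognostic marker than the protocol says. This stands in part. The crude test is valid for its hypothesis, and adjustment is a recommendation, not the repair of a contradiction. It does not remove the absence of an effect estimate for death or of an AUC with its interval, which even a modest reading of the objective calls for.

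A reader might go further and infer that a significant crude result would often be a false positive. The documents do not support that. One can assume that RDW adds nothing beyond severity, that it correlates 0.2 to 0.4 with severity, that severity has an odds ratio of 2 to 3 per SD, and that mortality is 20% to 80%. The crude test is then significant in about 8% to 46% of studies of 110, against 4% to 6% after adjustment. Every one of those inputs is invented, and the crude associations are real ones, so the figures do not measure an error in this plan.

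It may also be said that 110 patients are too few for an adjusted model. That is fair as to power, and it limits the model to very few terms. It is no reason to omit an estimate with its interval.

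The restriction to patients with at least three days in the ICU (sections 3 and 4) affects whom any result applies to, but it is a separate matter.

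**Conclusion.** The point holds as a cheap improvement. The planned analysis answers whether RDW differs by outcome. It does not report how the risk of death changes with RDW, how well RDW discriminates and with what precision, or what remains after allowing for severity.

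On the plan's own inputs, the difference it is sized to detect corresponds to an AUC of about 0.66, with a 95% interval of about 0.56 to 0.76 at best. A barely significant result would correspond to an AUC of 0.61 to 0.63. These figures rest on normality and on assumed mortality.

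It would be wrong to conclude that the primary test is invalid, that the sample size is miscalculated, or that the protocol claims independent prognostic value. It would also be wrong to say that the plan names RDW at ICU admission as its marker. That choice is assumed here, because the documents record both admission values and later trends without choosing.

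**What to change.** Add to section 6:
- Keep the t-test or Mann-Whitney test as the univariable result.
- State which RDW value is primary (ICU-admission RDW is assumed in this point).
- Fit a logistic regression of recorded mortality on continuous RDW. Report the odds ratio per 1% with its 95% interval, crude and adjusted for one covariate fixed before analysis. APACHE II is suggested: RDW plus APACHE II is two terms, and 22 patients in the smaller outcome group (deaths or survivors) gives 22/2 = 11 per term. The usual guide of about 10 per term is a rule of thumb that is not in the documents.
- Report the AUC with its 95% interval for RDW alone. The change in AUC when RDW is added to APACHE II is optional and descriptive.
- Claim value beyond severity only from the adjusted model.

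**Cost.** Some SAP wording and a little analysis time, with no new data. If the optional change in AUC is corrected for optimism by bootstrap, software other than the named SPSS version may be needed; the documents do not settle this.

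**Downside.** The adjusted estimate is less precise and may be less favourable than the crude one. Since 110 was sized for the crude comparison, no 80% power should be claimed for the adjusted test. Simulated adjusted power is about 45% to 75% over 20% to 80% mortality, if the adjusted log odds ratio is 0.58 per SD. That is optimistic: those scenarios imply crude power of about 74% to 99%, mostly above the planned 80%, and adjusted power would be lower if adjustment shrinks the effect. An approximate formula that holds the coefficient fixed gives 76% to 82% at 50% deaths, if age and severity scores explain 20% to 30% of the variance in RDW. The figure thus depends on what is assumed, and the adjusted result is best presented as an estimate with its interval.

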## 7. Ethical Considerations

- **Confidentiality:** All patient data will be de-identified and securely stored. Access to the data will be restricted to authorized research personnel only. The data will be kept in a secure database with access limited to the research team.
- **Risk to Participants:** Since this is a retrospective study utilizing existing medical records, there is no direct risk to participants. The study does not involve any intervention and does not cause any harm to patients whose records are analyzed.
- **Benefits:** The potential benefits of this study include a better understanding of prognostic markers in COVID-19, which may improve patient care and resource allocation in intensive care units. This could contribute to better patient outcomes and more efficient use of healthcare resources.
- **Informed Consent:** Given the retrospective design of the study and the use of de-identified data, obtaining informed consent from patients was not feasible. Since the study poses no more than minimal risk to participants and does not involve procedures for which written consent is normally required outside the research context, a waiver of informed consent was requested and approved by the ethics committee.
